8.9.1 Analysis of Primary Endpoints

The primary goal of this study is to evaluate the efficacy of the SPT to improve skinfold conditions, including erythema, maceration, denudation, satellite lesions, pain, itching, burning and odor over five days of treatment. Erythema, maceration, denudation, satellite lesions, and odor will be assessed using Likert scales, with "0" being least severe and "4" being most severe. Ordinal mixed models, or other appropriate methods depending on the distribution of data, will be employed to compare the assessment of skin fold

conditions of target areas across five days of treatment, with participants as a random variable and treatment days (Day 0, and Days 1, 3, and 5) as a covariate. Significant omnibus test will be followed by Tukey's post-hoc pairwise comparisons of Day 0 vs Day 1, Day 0 vs Day 3, Day 0 vs Day 5, Day 1 vs Day 3, and Day 3 vs Day 5.

ANOVA/Mixed models, or other appropriate methods depending on the distribution of data, will be conducted to compare VAS scores of discomfort (pain, itching, or burning) reported by participants on Day 0, and Days 1, 3, and 5. Significant omnibus test will be followed by Tukey's post-hoc pairwise comparisons of Day 0 vs Day 1, Day 0 vs Day 3, Day 0 vs Day 5, Day 1 vs Day 3, and Day 3 vs Day 5. In addition, descriptive statistics for the most prominent discomfort in the target area will also be reported in this study.

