8. STATISTICAL CONSIDERATIONS

8.1. Sample Size Determination

The sample size of 119 skin fold conditions was selected to detect a minimal clinically significant difference of 10 in the VAS pain scale between days of SPT changes with an estimated standard deviation of 30 and a Bonferroni adjusted α of $\alpha = .0083$ at 80% power, using the “Paired Wilcoxon Signed-Rank Test” procedure in PASS 2021 Power Analysis and Sample Size Software (2021). NCSS, LLC. Kaysville, Utah, USA, ncss.com/software/pass). It is noted that participants may have skin folds with independent skin fold conditions. One participant may be the source of, at most, two skin fold conditions for the purposes of this study. The candidate skin fold conditions must be, in the assessment of the PI or qualified designee, anatomically distant enough to permit objective assessment of discomfort (pain, itching, and burning) in each target area by the participant. In the event that a participant withdraws from the study, additional participants will be enrolled to achieve a final number of 119 target areas with complete data and until adequate power for analysis has been reached.

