8.5. Interim Analysis

Two interim analyses will be performed at 34% and 67% completion, testing for early efficacy or futility, using t-score boundaries that follow O’Brien-Fleming Analog alpha and beta spending rules. Assuming that the two interim analyses will occur after approximately 40 (1/3 of 119 total target areas) and 80 (2/3) target

areas have been assessed and adjudicated, the nominal alpha levels to reject the null hypotheses for efficacy are as follows in the table below.

Analysis Order	Number of Target Areas	Nominal critical point (Z-value)	Alpha level
1	40	-4.42	0.00000
2	80	-3.09	0.00122
Final	119	- 2.406	0.00804

Futility analyses are planned to be conducted to coincide in timing with the tentative interim analyses. The formal criterion for determination of futility is that at each interim look, if the condition power (defined as the probability of rejecting the null hypothesis at the final analysis given the data accumulated so far and under the assumption that the alternative hypothesis under the original design is true) falls below 20%, then the trial will be considered for stopping.

An interim monitoring tool, the most current version of PASS software will be used to estimate the conditional power.

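### The 80% power in Section 8.1 belongs to a test that Section 8.9.1 does not name, and no rule links the plan's three significance levels (.0083, 0.00804, .05)

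*Combined protocol and SAP*

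**What the plan says.** Four sections bear on how a day-to-day change in VAS pain is tested.

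- Section 8.1: N is 119, and the effect it is meant to pick up is a "minimal clinically significant difference of 10 in the VAS pain scale between days of SPT changes". The assumed SD is 30, the alpha is a Bonferroni-adjusted .0083 and the power is 80%. The procedure used was the "Paired Wilcoxon Signed-Rank Test". The divisor, the family of tests and the sidedness are not given.
- Section 8.5: "the nominal alpha levels to reject the null hypotheses for efficacy are as follows in the table below". The table ends at Z = -2.406 with alpha 0.00804 for 119 target areas. It names no test, endpoint or day pair.
- Section 8.9: P < .05 is the general criterion for significance.
- Section 8.9.1: VAS discomfort is compared across Days 0, 1, 3 and 5 by ANOVA or mixed models. Other methods are allowed if the distribution calls for them. A significant omnibus test leads to Tukey's "post-hoc pairwise comparisons of Day 0 vs Day 1, Day 0 vs Day 3, Day 0 vs Day 5", plus Day 1 vs Day 3 and Day 3 vs Day 5. Day 1 vs Day 5 is not listed.

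The Wilcoxon test is named only in Section 8.1.

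**The concern.** Power belongs to a particular test at a particular level. Here the powered test and the planned test differ, and the plan gives three levels without saying which one decides the final analysis. If 8.5 governs, its level is already Bonferroni-reduced, and Tukey would adjust for the day pairs again. If 8.9 governs, the final level in 8.5 is not used and the alpha spent at two efficacy looks is not carried forward. At stake are the correctness of the 80% figure and the threshold for declaring an effect. As written, that threshold could be settled after the data are seen.

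**Working it through.** **Inputs.** From 8.1: N = 119, difference 10, SD 30, alpha .0083, power 80%. From 8.5: final Z -2.406 and alpha 0.00804, with looks at about one third and two thirds. From 8.9: .05. From 8.9.1: four assessment days, omnibus test, then Tukey. Assumptions: SD 30 is the SD of paired differences, differences are normal, variances and correlations are equal across days, and target areas are independent. Power figures ignore the looks.

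**Step 1: reproduce 119.** A paired t-test for 10/30 at two-sided .0083 and 80% power needs n = 113 (noncentral t). The efficiency of the Wilcoxon test relative to the t-test for normal data is 3/π, so N = 113 × π/3 = 118.3, rounded up to 119. Power at 119 is 80.5%. A one-sided .0083 would give 98 × π/3 = 102.6, so 103. The stated figure is therefore right for its own test, and it is two-sided.

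**Step 2: source of .0083.** .05/6 = .00833, and four days give 4 × 3/2 = 6 pairs. The five pairs listed in 8.9.1 would give .05/5 = .01. A family of six day pairs fits both the number and the between-days wording of 8.1, but it is an inference.

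**Step 3: sidedness of 8.5.** The one-sided tail beyond 2.406 is 0.0081 (two-sided 0.0161), so 0.00804 is a one-sided level. O'Brien-Fleming-type spending at 1/3, 2/3 and 1 gives:

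| Total alpha | Look 1 | Look 2 | Final |
|---|---|---|---|
| .0083 one-sided | 4.42 | 3.03 | 2.41 |
| .0083 two-sided | 4.83 | 3.32 | 2.65 |
| Stated in 8.5 (absolute values) | 4.42 | 3.09 | 2.406 |

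So 8.5 uses .0083 one-sided and 8.1 uses it two-sided. Also, the stated 3.09 has a one-sided tail of 0.0010, while the stated 0.00122 needs about 3.03.

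**Step 4: power of the named procedure.** The noncentrality for one day pair is 10/(30/√119) = √119/3 = 3.636. The Tukey critical value is q/√2 for four means with 3 × 118 = 354 degrees of freedom. N for 80% is approximately [3 × (critical value + 0.8416)]², rounded up.

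| Level applied to Tukey-adjusted p | Critical t | Per-pair two-sided p | Power at 119 | N for 80% |
|---|---|---|---|---|
| .05 | 2.58 | .0102 | 85% | 106 |
| 0.00804 read one-sided (two-sided 0.0161) | 2.98 | .0031 | 74% | 132 |
| 0.00804 read two-sided | 3.20 | .0015 | 67% | 148 |

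In simulation (6,000 runs for each of three mean patterns) the omnibus gate costs less than 1 point at .05. In the same runs an unadjusted paired Wilcoxon at two-sided .0083 had 81% power.

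**Step 5: price of using .05 after two looks.** Four day means were simulated under no effect, with stopping at 4.42 and 3.09 on any day pair and a final Tukey test at .05. Family-wise error rises from .050 to about .053.

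**The case against.** The strongest reply is that .0083 in 8.1 is only a planning alpha. The .05 of 8.9 stands immediately before the Tukey plan and is the natural level for it. On that reading multiplicity is charged once, power is about 85%, Bonferroni sizing was merely cautious, and 119 is enough. The unlisted Day 1 vs Day 5 pair does no harm, since Tukey covers all six pairs. This much stands: the documents do not show the trial to be underpowered. It does not settle the matter, because 8.5 presents its levels as those for rejecting the null for efficacy, and 0.00804 is its level at the final analysis. Using .05 there contradicts 8.5, even though the inflation is small.

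A reader might infer four stronger points that the text does not support.

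- *The plan charges for the day pairs twice.* No section applies 0.00804 to Tukey-adjusted p-values. The double charge arises only if someone does so, and only if .0083 is .05 over six day pairs.
- *Power is 67%.* That figure takes 0.00804 as two-sided. Its Z-value marks it as one-sided, so 74% is the better figure for that reading.
- *The Wilcoxon test will never be run.* The open clause in 8.9.1 could admit it, but then the powered test is a data-dependent fallback.
- *Power is wasted without a single Day 0 vs Day 5 contrast.* At a full two-sided .05 with three looks such a contrast would have about 94% power. But 8.9.1 has eight primary outcomes. At .05/8 = .00625, a t-test of that contrast has about 80% before looks, so the gain depends on how alpha is shared. Section 8.1 itself is framed around differences between days.

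**Conclusion.** The point holds as a mismatch to be reconciled. The 80% in 8.1 is correct for a two-sided paired Wilcoxon test at .0083 but describes no analysis named in 8.9.1. The named procedure has about 85%, 74% or 67% power for one day pair, according to which level and sidedness are chosen, and the plan leaves that choice open. Sections 8.1 and 8.5 also differ in sidedness. These figures rest on the assumptions listed with the inputs. Correlation between two areas in one participant is not modelled.

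**What to change.** State in 8.5 and 8.9.1 one test for VAS pain, the same at both looks and at the final analysis, with one family of day pairs, one sidedness and one final alpha. Charge for day-pair multiplicity once, by one of two routes:

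- Tukey comparisons, with boundaries built on the undivided outcome-level alpha; or
- unadjusted day-pair contrasts, held to the Bonferroni-based boundaries.

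Then recompute the 8.5 table on that basis, so that each Z and alpha agree. State the divisor and family behind .0083 if it is kept, say that SD 30 refers to paired differences, and restate the 8.1 power for the chosen test.

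Naming Day 0 vs Day 5 (or last day) as the lead contrast, with other pairs supportive, is an option for the sponsor and not a required correction.

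The cost is wording, a new boundary table and one power calculation. Neither route by itself calls for more target areas: at N = 119 under these assumptions, Tukey at .05 has about 85% power, and an unadjusted Wilcoxon at two-sided .0083 about 80.5%. If the outcome-level alpha is set below .05 because of the eight outcomes, the Tukey figure falls and must be recalculated.

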8.9.2 Analysis of Secondary Endpoints

The secondary objective of this study is to gather PI or qualified designee assessment of moisture control in the target areas, as well as to assess HCP feedback about the SPT and overall participants experience with the SPT.

Moisture level in the target areas, evaluated by the PI or qualified designee using a Likert scale, will be compared across five days of treatment using ordinal mixed models. Appropriate descriptive statistics of moisture level of product, HCP feedback about the SPT, and overall participant experience with the SPT, based on the distribution and scale of the data, will also be reported.

9. SUPPORTING DOCUMENTATION AND OPERATIONAL CONSIDERATIONS

9.1. Clinical Monitoring

The Clinical Research Associate (CRA) will confirm that the rights and well-being of the participants are protected, and that the reported trial data are accurate, complete, and verifiable from source documents. Moreover, the CRA will confirm that the conduct of the trial by the PI and the site is in compliance with the protocol, GCP, and regulatory requirements as well as any applicable institution, ethical boards, and governmental processes. The first monitoring visit will be scheduled after the first participant has been enrolled. Thereafter, monitoring will occur per the Clinical Monitoring Plan (CMP), if available, or approximately every two months during the study duration or more frequently if:

- The volume or quantity of data is large or there is a backlog of review due to unexpected issues
- The site compliance with the protocol or compliance with expected ICH/GCP and regulatory requirements is lacking or there are continuing unresolved compliance issues
- There are unexpected ADE/SADE or participant safety concerns noted
- There are any unexpected inconsistencies with study product management
- There is a request for more frequent monitoring by the site
- Any mutually agreeable situation as determined by the site(s) and Medline

The frequency of routine monitoring may be increased to a longer interval depending on site enrollment. The CRA(s) will discuss this with Medline's Clinical Affairs Director or Manager, and will inform the PI prior to implementation.

Monitoring activities will include participant eligibility, source data review, CRF completion verification, product accountability, site continued suitability, PI study oversight, compliance, and all general monitoring activities as outlined in FDAs CFR and ICH/GCP guidelines that guide that activity.

Medline may, on occasion, contract with external Contract Research Organizations (CROs) to provide CRA services, and those CRAs are authorized to act on behalf of Medline.

It is expected that the site will be compliant with any institutional SOPs during the execution of the protocol and evidence of that compliance should be readily documented and verifiable by the CRA(s).

The CRA will provide the PI with a detailed follow-up letter after each monitoring visit that will outline the completed monitoring activities as well as any identified areas of concern and the expected/applicable corrections needed. Medline reserves the right to perform audit of the study activities – either routine or for-cause – as needed, and may perform a clinical monitoring audit as well.

9.2. Regulatory and Ethical Considerations

9.2.1. Confidentiality and Privacy

Participant confidentiality and privacy is strictly held in trust by the PI, the study staff, and the sponsor. Therefore, documentation, data, and all other information generated will be held in strict confidence. No information concerning the study or the data will be released to any unauthorized third party without prior written approval of the sponsor. All study data and study records will be managed and stored in accordance with the site's policies on data storage and security. All electronic transmission of data will adhere to Health Insurance Portability and Accountability Act (HIPAA) and any local regulations.

The study monitor, other authorized representatives of the sponsor, representatives of the IRB, and regulatory agencies may inspect all documents and records required to be maintained by the PI, including but not limited to, medical records (office, clinic, or hospital) and pharmacy records for the participants in this study. The clinical study site will permit access to such records.

A master list linking participant ID numbers to patient name and medical record number will be maintained in a secure database by the PI or paper files in secure cabinet(s). The participants' contact information will be securely stored at each clinical site for internal use during the study. The PI will agree to notify the sponsor of any intent to move or destroy these documents.

9.2.2. Safety Oversight

Safety oversight will consist of monitoring of visit activity, and ADEs and SADEs by the PI, who is suitably qualified and experienced to evaluate any ADEs or SADEs. The PI will review all ADEs and SADEs and make any necessary safety determinations or visit activity modifications that are in the best interest of the participant as necessary. See also Section 7 for reporting and management requirements.

9.2.3. Study Discontinuation

The study may be temporarily suspended or prematurely terminated if there is sufficient reasonable cause. Written notification, documenting the reason for study suspension or termination, will be provided by the suspending or terminating party to the PI, sponsor, and the IRB. If the study is prematurely terminated or

suspended, the PI, in collaboration with the sponsor, will promptly inform the IRB and will provide the reason(s) for the termination or suspension.

Circumstance(s) that may warrant termination or suspension include, but are not limited to:

- Determination of unexpected, significant, or unacceptable risk to participants as determined by AE review
- Insufficient compliance to protocol requirements
- Data that are not sufficiently complete and/or evaluable

The study may resume once concerns about safety, protocol compliance, and data quality are addressed, and the sponsor and/or the IRB are satisfied.

9.2.4. Study Closeout

Upon completion of the study, Medline and/or its designees will notify the site of closeout-related procedures and will coordinate with the site the return of equipment and/or any unused product. Medline CRA(s) will communicate closely with the PI at that time point and will review all closeout steps and materials. All study data, related study documents, and unused study product, will be returned to the sponsor or as per agreement with the study contract. The site will also notify the IRB that the study has been completed.

9.2.5. Data Handling and Record Keeping

Data collection is the responsibility of the research staff at the site under the supervision of the PI. The PI is responsible for ensuring the accuracy, completeness, legibility, and timeliness of the data reported in the CRFs or any other study activity documentation as part of this study. All the documents should be completed in accordance with GDP to ensure accurate interpretation of data.

Final storage of Medline data will be per ICH/GCP guidelines in a protected access area for the length of the time required.

9.2.6. Conflict of Interest Policy

The independence of the study from any actual or perceived influence is critical. Therefore, any actual conflict of interest of persons who have a role in the design, conduct, analysis, publication, or any aspect of the study will be disclosed and managed.

9.3. Protocol Deviations

It is the responsibility of the PI and qualified designee to use continuous vigilance to identify and report deviations on a routine basis. All deviations must be addressed in the study source documents and reported to Medline. Protocol deviations must be sent to the reviewing IRB per reporting requirements and should be reported to the sponsor in a timely manner. The PI is responsible for knowing and adhering to the reviewing IRB requirements.

9.4. Abbreviations

ADE	Adverse Device Event
-----	----------------------

CFR	Code of Federal Regulations
CMP	Clinical Monitoring Plan
CRA	Clinical Research Associate
CRF	Case Report Form
CRO	Contract Research Organization
FDA	Food and Drug Administration
GCP	Good Clinical Practices
GDP	Good Documentation Practices
HCP	Healthcare Provider
HIPAA	Health Insurance Portability and Accountability Act
ICF	Informed Consent Form
ICH	International Conference on Harmonisation
ICU	Intensive Care Unit
ID	Identification
IFU	Instructions for Use
IRB	Institutional Review Board
LP	Limited Partnership
MRSA	Methicillin-Resistant Staphylococcus aureus
PI	Principal Investigator
PSF	Participant Screening Form
SAE	Serious Adverse Event
SADE	Serious Adverse Device Event
SPT	Skin Protectant Textile
SOA	Schedule of Activities
UADE	Unanticipated Adverse Device Effect
US	United States

VAS

Visual Analogue Scale

